17. ETHICAL CONSIDERATIONS

The trial will be performed in accordance with the recommendations guiding physicians in biomedical research involving human subjects, adopted by the 18th World Medical Association General Assembly, Helsinki, Finland, 1964, amended by the 48th WMA General Assembly, Somerset West, Republic of South Africa, 1996 (website: <http://www.wma.net/en/30publications/10policies/b3/index.html>).

The trial will be conducted in accordance with the Research Governance Framework for Health and Social Care, the applicable UK Statutory Instruments, (which include the Data Protection Act 1998) and the Principles of GCP. The protocol will be submitted to and approved by the main REC prior to circulation.

Before any participants are enrolled into the trial, the PI at each site will obtain local R&D approval/assurance. Sites will not be permitted to enrol participants until written confirmation of R&D approval/assurance is received by the BCTU trials team.

It is the responsibility of the PI to ensure that all subsequent amendments gain the necessary local approval. This does not affect the individual clinicians' responsibility to take immediate action if thought necessary to protect the health and interest of individual participants.

18. CONFIDENTIALITY AND DATA PROTECTION

Personal data recorded on all documents will be regarded as strictly confidential and will be handled and stored in accordance with the Data Protection Act 1998.

Participants will always be identified using their unique trial identification number and partial date of birth (month / year) on the Case Report Form and correspondence between BCTU and local centres. Participants will give their explicit consent for the movement of their consent form, giving permission for BCTU to be sent a copy. This will be used to perform in-house monitoring of the consent process".

The Investigator must maintain documents not for submission to BCTU (e.g. Participant Identification Logs) in strict confidence. In the case of specific issues and/or queries from the regulatory authorities, it will be necessary to have access to the complete trial records, provided that participant confidentiality is protected.

BCTU will maintain the confidentiality of all participant's data and will not disclose information by which participants may be identified to any third party other than those directly involved in the treatment of the participant and organisations for which the participant has given explicit consent for data transfer (e.g. laboratory staff, competent authority, sponsor). Representatives of the LAVA trial team and sponsor may be required to have access to participant's notes for quality assurance purposes but participants should be reassured that their confidentiality will be respected at all times.

19. Financial and other competing interests

Members of the TMG or study oversight committees will be required to declare any financial or other competing interests. These will be recorded in specific documents recording any competing interests based upon the DAMOCLES declaration.

20. Insurance and Indemnity

The University of Birmingham has in place Clinical Trials indemnity coverage for this trial which provides cover to the University for harm which comes about through the University's,

or its staff's, negligence in relation to the design or management of the trial and may alternatively, and at the University's discretion provide cover for non-negligent harm to participants.

With respect to the conduct of the trial at Site and other clinical care of the patient, responsibility for the care of the patients remains with the NHS organisation responsible for the Clinical Site and is therefore indemnified through the NHS Litigation Authority.

The University of Birmingham is independent of any pharmaceutical company, and as such it is not covered by the Association of the British Pharmaceutical Industry (ABPI) guidelines for participant compensation.

21. Amendments

The decision to amend the protocol and associated trial documentation will be initiated by the TMG. As sponsor, The University of Birmingham will be responsible for deciding whether an amendment is substantial or non-substantial. Substantive changes will be submitted to REC for approval. Once this has been received, R&D departments will be notified of the amendment and requested to provide their approval. If no response is received within 35 days, an assumption will be made that the site has no objection to the amendment and it will be implemented at the site. All amendments will be tracked in the 'Protocol Amendments' section of the protocol.

22. Post-trial care

All patients will continue to receive standard medical care following participation in the clinical trial. There are no interventions that participant's will be prevented from accessing after their participation in the trial has been completed.

23. Access to the final trial dataset

During the period of the study only the trial steering group will have access to the full trial dataset in order to ensure that the overall results are not disclosed by an individual trial site prior to the main publication.

Following publication of the findings, the final trial dataset will be made available to external researchers upon approval from the trial management group and the BCTU data sharing committee in line with standard data sharing practices for clinical trial data sets.

24. Publication Policy

Results of this trial will be submitted for publication in a peer reviewed journal. The manuscript will be prepared by the CI and authorship will be determined by the trial publication policy.

Any secondary publications and presentations prepared by Investigators must be reviewed and approved by the TMG prior to wider circulation. Manuscripts must be submitted to the TMG in a timely fashion and well in advance of being submitted for publication to allow time for review and resolution of any outstanding issues.

Authors must acknowledge that the trial was performed with the support of the University of Birmingham and Birmingham Clinical Trials Unit. Intellectual property rights will be addressed in the Clinical Study Site Agreement between Sponsor and site.

The trial question is important and has the potential to change clinical practice. This view has been validated by the health professionals and patient surveys that have been conducted by our research team and from research recommendations arising from systematic reviews and national, evidence-based guidelines. We have prioritised methods to ensure rapid, clinical impact once the results of the LAVA trial are available. These include:

Guidelines: The information is expected to be rapidly incorporated into guidelines by the Royal College of Obstetricians and Gynaecologists (RCOG), the British Society of Gynaecological Endoscopy (BSGE), the National Institute of Health and Care Excellence (NICE) and international guidelines and disseminated nationally for implementation. This will be facilitated by the coinvestigator group who hold senior positions in many of these bodies.

All current systematic reviews and guidance have acknowledged the need for research and we therefore believe that authors will be receptive to these new findings

Patient information resources: Production of lay information with links to appropriate patient organisations, particularly the Hysterectomy Association and the RCOG (RCOG Women's Voices and patient information department). With our PPI co-applicants and contacts we will produce effective, contemporary formats for dissemination e.g. the use of video podcasts and social media outlets.

Conferences: The findings will be presented and disseminated via the BSGE, RCOG and other national and international conferences.

Peer reviewed publications: We will aim to publish the findings in high impact peer reviewed journals. We will disseminate the completed paper to the Department of Health, the Scientific Advisory Committees of the RCOG, the Royal College of Nurses (RCN) and the BSGE.

NIHR Journals Library: A copy of the monograph will be lodged with the NIHR Journals Library will help with dissemination of findings and will provide an important, permanent and comprehensive record of the study.

Media: In consultation with the investigators and appropriate journal, a press release will be issued to the media upon publication of the results.

26. APPENDICES

26.1 Appendix 1: Trial Schema

LAVA TRIAL				
PHASE	Population Women with a benign gynaecological condition requiring a hysterectomy who are suitable for either laparoscopic or abdominal approaches	TIMESCALE		
Recruitment	Assessed for eligibility			
	Informed consent Baseline assessment	BASELINE (Internal pilot with embedded qualitative evaluation during first 9 months)		
	Randomisation n = 3250			
Intervention	
 
 Laparoscopic hysterectomy n = 1625	Abdominal hysterectomy n = 1625	
 
	Laparoscopic hysterectomy n = 1625	Abdominal hysterectomy n = 1625	Surgery
Laparoscopic hysterectomy n = 1625	Abdominal hysterectomy n = 1625			
Outcome assessment	Primary Outcome Major complications (up to 6 weeks)			
	Secondary Outcomes Time to resumption of usual activities ¹ , surgical duration, blood loss, complications, quality of recovery ² , pain ³ , readmission / representation ⁴ , quality of life, work participation and use of clinical care services (economic)	6 and 12 weeks (post-surgery)		
	Secondary Outcomes Satisfaction, new gynaecological symptoms, urogenital prolapse, bowel / bladder functioning, body image, sexual activity, quality of life, SAEs, use of clinical care services (economic)	12 months (post-surgery)		
	Longer term Secondary Outcomes Satisfaction, new gynaecological symptoms, urogenital prolapse, bowel / bladder functioning, body image, sexual activity, quality of life, SAEs, use of clinical care services (economic)	24 & 36 months (post-surgery) ⁵		

¹ Time from surgery to resumption of usual activities will continue to be evaluated until all 8 selected activities have been resumed

² 24 hours post-surgery

³ Daily, up to and including 14 days post-surgery

⁴ 6 weeks post-surgery only

⁵ Restricted to subgroups of participants reaching these timepoints prior to close of the study i.e. when the last randomised patient reaches 12 months post-surgery

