3.4.2. Health Economic evaluation

An economic evaluation alongside the RCT will explore the cost-effectiveness of laparoscopic hysterectomy compared to open abdominal hysterectomy based on a primary outcome of quality-adjusted life years and secondary outcomes such as major surgical complications avoided. The analysis will adopt the perspective of the health service. All resource use will be collected prospectively and unit costs attached. Deterministic and probabilistic sensitivity analysis will be carried out.

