8.1.3.2 Other secondary outcomes

- Surgical outcomes:
 - Duration of operation, (minutes)
 - Estimated blood loss, (ml)
- In hospital stay:
 - In hospital post-operative pain using a Numerical rating scale (NRS) (with 0 indicating no pain to 10 indicating maximum pain)*, measured daily
 - Total analgesia use*
 - Overall quality of recovery score taken from the Quality of Recovery 15 (QoR-15) questionnaire²⁵ (with 0 indicating worst recovery and 10 indicating best recovery), measured at approximately 24 hours post-operation*
 - Time from operation to discharge in days (the day of operation will be assumed to be day 1. i.e. discharge on day 2 = 2 days). Each part of a day will count as a whole day, e.g. discharge after 2.5 days = 3 days)
- Up to 14 days after surgery:
 - post-operative pain using a Numerical rating scale (NRS) (with 0 indicating no pain to 10 indicating maximum pain), measured daily
 - Total analgesia use

- Up to 6 weeks post-surgery:
 - Minor complications (Haemorrhage 500mL to ≤ 1 L; pyrexia [presumed infection] requiring antibiotics; pain uncontrolled with usual analgesic management; urinary retention requiring re-catheterization; catheterisation for longer than 72 hrs; pelvic haematoma NOT requiring radiological or surgical intervention; pelvic abscess NOT requiring radiological or surgical intervention; wound infections/complications managed at the bedside or on the ward)
 - Representation to hospital
 - Readmission to hospital
 - Use of health services
 - Time away from normal activities

- 6 weeks post-surgery:
 - Quality of life score using EuroQol-5D-5L questionnaire²⁶ (with -0.285 indicating worst possible value and 1.0 as best possible value)
 - Quality of life score using EuroQol-5D-5L visual analogue scale (with 0 indicating worst possible score and 100 as best possible score)

- 12 weeks post-surgery:
 - Quality of life score using EuroQol-5D-5L questionnaire²⁶ (with -0.285 indicating worst possible value and 1.0 as best possible value)
 - Quality of life score using EuroQol-5D-5L visual analogue scale (with 0 indicating worst possible score and 100 as best possible score)
 - Time from surgery to work (if working) in days
 - Work productivity and activity impairment scores using WPAI-GH questionnaire²⁷ (absenteeism score; presenteeism score; work productivity loss score; activity impairment score – all scored 0 good to 100 bad) at 12 weeks only

- 12/24/36 months post-surgery:**

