8.2.8. At home week 12 post-surgery **

- Quality of life score and work assessment ("12 week follow up CRF")
 - EuroQol-5D-5L and VAS
 - Time from surgery to work (if working) and work productivity and activity impairment scores using WPAI-GH questionnaire

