8.2.10. Summary of schedule of assessments

Visit	Pre-randomisation		Rand	Surgery	Post-surgery						
	Screening and recruitment	Baseline		Surgery	Hospital stay	Day 2-14	Weekly Week 1 to 12 (inc)	6 weeks + 28 days	12 weeks + 28 days	Fortnightly weeks 13 to 26 (inc)	Month 12 + 6 months **
Eligibility check	x										
Valid informed consent	x										
Baseline demographic and medical questionnaire		x									
Urogenital Distress Inventory (UDI)		x									x
Defecatory Distress Inventory (DDI)		x									x
Sexual Activity Questionnaire (SAQ)		x									x
EuroQol (EQ-5D-5L and EQ VAS)		x						x	x		x
Patient-Reported Outcomes Measurement Information System Physical Function (PROMIS-PF)		x					x			x	
Randomisation			x								
Surgery CRF				x							
Resource use CRF					x						

Pain (Numerical Rating Scale - NRS) & analgesia questionnaire					X						
Time to discharge & complications					X						
Quality of Recovery-15 questionnaire*					X						
Pain (NRS) symptom diary						X					
Six week post-surgery questionnaire including health care utilisation								X			
Work questionnaire / Work Productivity and Activity Impairment Questionnaire (WPAI-GH)									X		
Six week post-surgery complication and representation form								X			
Satisfaction with hysterectomy											X
New gynae symptoms											X
Pelvic organ prolapse quantifications – POP-SS		X									X
Body Image Scale (BIS)											X
Contact with Community Social and Clinical Care Services form											X
Serious Adverse Events				X	X	X	X	X	X	X	X

* *If patient discharged as a day-case then they should be instructed to complete at home at 24 hours post-surgery*

****** *The same 12 month post-surgery questionnaires will be sent to all participants reaching 24 and 36 months of follow up post-surgery, prior to close of the LAVA study; defined as when the last randomised patient reaches 12 months follow up post-surgery*

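### The schema's pooled 6-and-12-week box includes service use, but the forms collect it only at week 6 and then at 12 months, so later self-reported costs rest on one long-recall form

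*Protocol*

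**What the plan says.** The early secondary-outcome box of the schema (Protocol, Appendix 26.1) ends with "quality of life, work participation and use of clinical care services (economic") and is timed "6 and 12 weeks (post-surgery"). Footnote 4, "6 weeks post-surgery only", is attached to readmission and representation. Service use carries no footnote.

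The body of the protocol is narrower:

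- Section 8.1.3.2 lists "Use of health services" among the outcomes up to 6 weeks and not among the 12-week outcomes.
- Section 8.2.7 puts it on the 6-week participant form. Section 8.2.8, the 12-week form, has EQ-5D-5L with its VAS and "Time from surgery to work (if working) and work productivity and activity impairment scores using WPAI-GH questionnaire", and nothing on service use.
- Section 8.2.10 marks the row "Six week post-surgery questionnaire including health care utilisation" in the 6-week column only. The form on contacts with community and clinical services is marked only in the column headed "Month 12 + 6 months".

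Section 15 makes cost per QALY over 12 months the principal economic outcome. It says that follow-up care to 12 months will be collected on case report forms. Section 3.4.2 states: "All resource use will be collected prospectively and unit costs attached".

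**The concern.** Section 15 wants outpatient and emergency visits, re-presentations, re-admissions and primary-care contacts costed over 12 months. Between week 6 and month 12 the schedule has no form that asks about them. EQ-5D is measured at week 12, so the QALY side of the ratio has a data point there and the cost side has none.

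Three things are at stake:

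- **Recall.** Brief contacts, such as a GP or nurse consultation, have to be remembered over most of a year or longer.
- **Missing data.** A woman who returns the 12-week form but not the 12-month form gives no self-reported service use after week 6.
- **Horizon.** The 12-month form may be completed up to six months late, and the protocol states no cut-off for the contacts to be reported on it. Contacts from months 12 to 18 could therefore be counted in a 12-month cost.

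**Working it through.** The protocol states no recall length, so there is no figure of its own to reproduce. The check has two parts.

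**Part 1: where service use is collected**

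| Place in the protocol | Week 6 | Week 12 | Month 12 |
|---|---|---|---|
| Schema, 26.1 | yes (pooled box) | yes (pooled box) | yes |
| Outcome list, 8.1.3.2 | yes | no | yes |
| Participant forms, 8.2.7 to 8.2.9 | yes | no | yes |
| Schedule table, 8.2.10 | yes | no | yes |

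Other possible sources between week 6 and month 12:

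- The site form on complications and representation (8.1.2) stops at 6 weeks.
- Serious adverse events are recorded throughout, but Section 9.2 takes emergency presentations and admissions out of adverse event reporting. They cannot stand in for a service-use record.

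On the schedule, therefore, service use after week 6 comes from the 12-month contact form, apart from those serious adverse events that remain reportable.

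**Part 2: length of the look-back**

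Inputs:

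- The early coverage ends at week 6, which is 42 days (8.1.3.2).
- The 12-month form may be completed from month 12 to month 18 (8.2.10).
- The 12-week form may be completed from week 12 to week 12 plus 28 days (8.2.10).
- One month is 365.25/12 = 30.44 days.

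Formula: look-back = (date of form − end of previous coverage) / 30.44.

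- Form at month 12: (365.25 − 42)/30.44 = 10.6 months. In weeks, 52 − 6 = 46.
- Form at month 18: 10.6 + 6 = 16.6 months. In weeks, 78 − 6 = 72.
- If the 6-week form came back on the last day of its 28-day window and also covered those days, the start would be day 70. The look-back would then be (365.25 − 70)/30.44 = 9.7 months, or 15.7 months at the end of the window. The outcome is defined as up to 6 weeks, so 10.6 to 16.6 is the better reading.

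With service-use items added at week 12:

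- Weeks 6 to 12 are recalled over 12 − 6 = 6 weeks, or 16 − 6 = 10 weeks if the form is returned at the end of its window.
- The longest look-back becomes (365.25 − 84)/30.44 = 9.2 months, or 15.2 months at month 18.
- The share of the 12-month horizon resting on the 12-month form falls from (365.25 − 42)/365.25 = 88.5%, about 89%, to (365.25 − 84)/365.25 = 77%.
- A woman who misses the 12-month form but returns the 12-week form contributes 12 weeks of self-reported cost data instead of 6.

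**The case against.** The strongest reply is that the schema proves little. Its box is a pooled label. Surgical duration and blood loss, which belong to the day of surgery, sit in it without a footnote. So does work participation, whose questionnaire is given at 12 weeks only. The missing footnote on service use is therefore weak evidence, and the timing can be read as 6 and/or 12 weeks. The outcome list, the forms and the schedule agree with one another, and a schema footnote would remove the mismatch. This stands. A reader might infer that a 12-week collection was planned and then dropped from the form, but the documents do not support that.

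Three other stronger readings also go too far:

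- **That one late form contradicts the promise of prospective collection.** A scheduled questionnaire within a trial can fairly be called prospective even when it asks about past contacts.
- **That contacts after month 12 will enter the 12-month cost.** Section 15 describes collection up to 12 months, and the form's wording and the costing rules are not shown. What can be said is that the protocol states no date limit for a form with a six-month window.
- **That the total cost rests on one form.** The procedure, the inpatient stay and complications and re-attendances to week 6 are captured earlier by site forms. The point concerns later costs only.

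It can also be said that Section 15 speaks of case report forms in the plural, that Section 10.1 allows interview for economic data, and that Section 10.3 lets staff query missing answers. These may improve completeness. They do not add a scheduled collection between week 6 and month 12.

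Finally, adding week 12 shortens the longest look-back by only about 1.4 months (10.6 − 9.2). That is true, and it limits what the remedy can claim.

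**Conclusion.** The mismatch is real and should be reconciled, whichever timing was meant. The design consequence holds in bounded form: as scheduled, self-reported service use after week 6, about 89% of the 12-month horizon by time, depends on one form with a look-back of up to 10.6 to 16.6 months.

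This rests on four assumptions:

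- The range is inferred from visit windows, and the recall question itself may be shorter.
- It applies to the oldest contact. The upper end applies only to a form returned on the last day of its window.
- The 6-week form covers contacts up to week 6 and no later.
- The 12-month horizon runs from surgery. Section 15 also once counts it from randomisation.

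The protocol gives no contact rates, costs after week 6 or questionnaire response rates, so the effect on the cost-effectiveness result cannot be quantified. The primary and key secondary clinical outcomes are unaffected. The change is worth making because it is cheap and bears on the principal economic outcome.

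**What to change.** 1. Add the existing 6-week service-use items to the 12-week form, asking for contacts since the 6-week form.
2. Align 8.1.3.2, 8.2.8, 8.2.10 and the schema so that all four give the same time points.
3. Have the 12-month form ask only for contacts since week 12 and up to the 12-month date, whenever it is completed. Section 8.2.10 sends the same questionnaire at 24 and 36 months, so the recall wording at those times needs its own limits.

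The cost is a short block of questions on a questionnaire already sent to every woman, and a minor amendment. The downside is a few more questions at week 12. Steps 1 and 2 give short recall for weeks 6 to 12 and preserve 12 weeks of cost data for women who miss the later form. Step 3 keeps contacts after month 12 out of the 12-month cost. Long recall from week 12 onwards remains.

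If the sponsor prefers not to collect at week 12, the schema should be footnoted to say so. Step 3 should still be made, with week 6 as the starting point.
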